5.2.4 Drug-drug interactions

Drug-drug interactions are relevant in patients with brain tumors, who take concomitant medications such as dexamethasone and chemotherapies that are metabolized via the CYP450 system. Older generation AEDs that are enzyme-inducing AEDs (EIAEDs) increase clearance of chemotherapy and dexamethasone, reducing efficacy, while other AEDs that are enzyme inhibitors potentially increase the toxicity of chemotherapies^{35,36}. In addition, AEDs themselves can build to toxic levels due to the drug-drug interactions, requiring more therapeutic monitoring of AED levels in these older generation drugs³⁵. Such issues are alleviated with LCM and LEV.

LCM has low potential for pharmacokinetic drug-drug interactions due to its low protein binding, which minimizes potential displacement of other drugs and because it does not inhibit or induce any of the CYP isoenzymes in a clinically relevant manner^{23,37,38}. LEV also has no known significant pharmacokinetic interactions since it is not metabolized through the liver^{13,27}.

5.2.5 Adverse Events

Lacosamide. LCM's most common adverse events (AEs) based on phase IIB/III trials in partial-onset seizures were related to central nervous system (CNS) and gastrointestinal effects^{39,40}. Dizziness, headache, nausea and diplopia were the most common in a pooled analyses of the trials, occurring at ≥10% in all doses combined (200-600mg/day, N=944)⁴¹. Other less common AEs included nystagmus, ataxia, vomiting, fatigue, somnolence, and headache^{39,40,42}. Incidence appeared dose related, more apparent during the initial titration phase, and less frequent during the maintenance phase¹⁴. The most common AEs that led to discontinuation of the drug were dizziness and abnormal coordination, and these occurred at the higher dose of 600mg/day⁴². There were no serious safety concerns regarding hematologic or clinical chemistry values identified⁴². Moreover, another meta-analysis of 10 randomized controlled trials of LCM for various indications determined LCM was not associated with any apparent adverse effect on cognition⁴³.

Levetiracetam. LEV is well tolerated; however, it can cause behavioral AEs such as aggression, irritability, and anger, as well as somnolence and cognitive side effects. Behavioral AEs reportedly occur in approximately 13% of patients, but up to 30% for some AEs such as irritability or anxiety⁴⁴. It has been associated with suicidal tendency and has a contraindication for use in patients with past history of psychiatric illness⁴⁵.

5.2.6 Efficacy in Epilepsy

Lacosamide. LCM was FDA approved as adjunctive therapy and monotherapy for partial-onset seizures (POS) in adults in 2008 and 2014, respectively¹⁰.

LCM is well known to be effective and well tolerated as an adjunctive agent for drug-resistant partial epilepsy, especially when combined with a non-sodium channel drug⁴⁶. This has been demonstrated in at least three

randomized controlled trials, as well as other studies²¹. More relevant to this study, it was more safe and efficacious to add LCM in patients who had breakthrough seizures on low dose LEV (<1500mg/day) than to increase the dose of LEV and thus increase the risk of behavioral side effects⁴⁷.

Studies have been very supportive of LCM's efficacy and safety as monotherapy in POS. A retrospective review of 66 patients across 6 centers with POS treated with LCM monotherapy revealed that 63.6% (42/66) remained seizure-free during follow up (up to 54 months)⁴⁸. The patients were grouped into those who had LCM as first line therapy (n=18) and those who had previously been treated with an AED (n=48). No difference in efficacy between the two groups in terms of outcomes or tolerability was found. Only 3/66 (4.5%) of patients had to discontinue therapy due to side effects, which were generally mild⁴⁸. Another study prospectively followed patients who were converted to LCM monotherapy after 1-year seizure freedom on LCM add-on therapy, followed by withdrawal of the concomitant AED⁴⁹. 55.2% (32/58) patients were seizure free at one year from withdrawal of the background AED, with those who were on more than three lifetime AEDs more likely to have a seizure⁴⁹. Side effects were mild to moderate in 20% (12/58) of patients⁴⁹. This study was performed on patients with POS with or without generalization⁴⁹. Other studies, including double-blind studies, have also supported the effectiveness and safety of conversion to LCM monotherapy after withdrawal of background AEDs⁵⁰.

In terms of generalized epilepsy, there have been studies to demonstrate LCM therapy being effective in these patients⁵¹, and studies are still ongoing to verify this (NCT01969851, NCT02408549).

Levetiracetam. LEV was FDA approved in 1999 as adjunctive therapy for POS in adults with refractory generalized myoclonic seizures¹¹. Since then, LEV is widely used for POS, general tonic-clonic (GTC) seizures, and generalized myoclonic seizures based on studies demonstrating its efficacy as adjunctive and monotherapy in these patients^{39,52-60}. The 2013 International League Against Epilepsy (ILAE) updated review on epilepsy stated that LEV has level A evidence as a monotherapy for POS in adults and Level D evidence as a monotherapy for newly diagnosed or untreated GTCs⁶¹. This was based on trials showing non-inferiority compared to carbamazepine (CBZ), the prior first line therapy for POS⁵⁷.

A recent prospective, open-label, randomized study further supported LEV monotherapy as non-inferior to CBZ in POS, resulting in 71 vs. 78% seizure freedom at 6 months (p=0.253). They were both well tolerated, but LEV had a better overall quality of life (QOL), measured by the QOL in Epilepsy (QOLIE)-10 questionnaire. However, LEV was associated with more behavioral changes, such as aggression and anxiety^{45,57,62}.

5.2.7 Efficacy in Brain Tumors

Seizures associated with brain tumors belong to the category of POS, either with or without secondary generalization⁶³. Since it is relatively new, there is limited data on LCM in brain tumors. Current data supports its tolerability and efficacy as an add-on agent⁶⁴. One retrospective analysis of 70 patients with primary brain tumors reported a decrease in seizure frequency in 66% (47/70) of patients⁶⁵. There are currently ongoing randomized, double-blind, placebo-controlled trials of LCM for seizure prophylaxis in patients with high grade gliomas (NCT01432171), and one as adjunctive therapy to refractory epilepsy in patients with low grade glioma (LGG) (NCT02276053). Its related side effects are the same as in non-brain tumor patients, mainly dizziness at high doses⁶⁵.

LEV, on the other hand, has evidence to support its use as a first line agent in brain tumors, due to its efficacy, low drug-drug interactions, and tolerability⁶⁶⁻⁶⁸. Seizure freedom with LEV has ranged from 76-91% with seizure reduction by half in 100% of patients^{3,67-69}. Recent studies have also shown it has a potential anti-tumor effect as an added benefit secondary to its role as an MGMT inhibitor, although this role has been contested with later analyses and is still being studied (NCT02815410)²⁰. Its risk of emotional instability (aggression, depression or irritability) is about the same 5-13% risk as in non-brain tumor patients, with a reported 0.4% incidence of psychosis 4 weeks after initiating LEV^{67,69}.

5.2.8 Clinical Experience

In our institution's experience, peri-operative LEV prophylaxis at a dose of 500mg BID was well tolerated among patients, with a 10% rate of AEs, mainly irritability, agitation and fatigue. At that dose, there was not a statistically significant reduction in post-operative seizure rates (34.6% seizure rate at this dose of LEV) among patients with newly-diagnosed high-grade gliomas (Pro00047350 Descriptive and Cost Analysis of Post-Operative Anti-Epileptic Drugs in Malignant Glioma). However, subsequent to the year studied, patients were initiated on 1000mg BID.

The goal of this study is to evaluate the impact of LCM, LEV or no AED on the re-admission rate and number of emergency room visits in the post-procedure period. If the use of an AED is shown to be beneficial, it is possible that LCM could be a preferable alternative for some patients, especially for those who do not tolerate LEV due to the behavioral side effects.

5.2.9 Study Purpose and Rationale

The primary purpose of this study is to evaluate 30-day readmission rates and ED visits through randomizing subjects to "no AED" or to the 2 primary AEDs used in this patient population here at DUMC.

Current guidelines recommend against peri-operative seizure prophylaxis for patients with newly diagnosed brain tumors; however, they were based on older generation AEDs that were associated with severe toxicities and drug-drug interactions. In light of newer generation AEDs with more tolerable safety profiles, some neurosurgeons and neuro-oncologists prescribe AEDs to patients for prolonged periods of time after surgery, despite these guidelines; this has also been the practice here at DUMC. Given the lack of recommendation for AED prophylaxis in the peri-operative period by the neurosurgical guidelines, which is contrary to Duke's practice, and given the cost and potential side effects of AEDs, it was determined that it is now time to formally assess the impact and side effect profile of the use or not of AEDs. If determined that AED is necessary, this study will also attempt to evaluate the side effect profile of the commonly used AED at Duke (levetiracetam) versus a newer AED (lacosamide).

The question most relevant to Duke neurosurgeons is the rate of readmission and ED visits after a Maximum Safe Resection (MSR) (gross-total, sub-total or biopsy), a measurable patient outcome to their surgery. If there is benefit on these rates from having an AED, that would provide support for neurosurgeons to prescribe AEDs. If there is no difference in readmission rates/ED visits between those who did and did not receive an AED, then there would be much more support against AED prophylaxis. If the adverse side effects of the AEDs studied are significant, then there will be a greater consideration of risk to benefit.

The risks of seizures in the perioperative period are very small, which is supported by the current guidelines recommending against seizure prophylaxis in the peri-operative period and further demonstrated by the incidence of peri-operative seizure of 34.6% observed in the Duke retrospective review (Pro00047350 Descriptive and Cost Analysis of Post-Operative Anti-Epileptic Drugs in Malignant Glioma). Thus, variables related to seizure incidence from use of AEDs all are important to study, but written as exploratory variables in this protocol. The data from this latter analysis may be suggestive of the impact of AED prophylaxis on seizure outcomes, but it is unclear at this point how significant the outcomes will be based on our knowledge of seizure rates. The outcome of this study may, therefore, impact Duke practice.

Overall, given the paucity of studies in the literature evaluating this question, it would have a significant contribution to outstanding literature and implications for standards in general, although the goal of this protocol is not to modify or update the general standard.

The benefit of a prospective, randomized study is to remove the bias that occurs in an observational study because the latter allows neurosurgeons to let their own practice/biases decide whether a patient should receive AED treatment and which type.

LEV and LCM are newer generation AEDs with better safety and tolerability than first generation AEDs, and studies lean towards their effectiveness in patients with POS, which affect a great deal of patients with primary brain tumors. LEV, a second generation AED, has been often used in these patients, but its side effects of irritability, somnolence, and rarely, psychosis, may be limiting for these patients already affected by cognitive and behavioral issues as a result of their tumors. LCM is a third generation FDA-approved AED for POS, and initial studies have shown its effectiveness as monotherapy after patients have failed and been weaned off other AEDs. Its safety and tolerability has been demonstrated in brain tumor patients, but studies evaluating the efficacy of LCM in this population are still lacking.

In this protocol, we will assess optimal seizure prophylaxis management during the post-procedure period for patients undergoing MSR for suspected diagnosis of new, recurrent, or transformed glioma (WHO grade I-IV) or brain metastasis. This will be determined by observing the impact of LCM, LEV, or no AED on whether visits to the emergency department (ED) or hospital re-admissions occur within 30 days after MSR. A secondary endpoint will evaluate the safety and tolerability of LCM and LEV. Exploratory endpoints will evaluate admission duration for the MSR, number of post-procedure provider communications (telephone, email, and additional clinic encounters, etc.), and patient risk factors associated with post-procedure seizure.

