6 OBJECTIVES AND ENDPOINTS

Table 1: Objectives and Endpoints

	Objective	Endpoint	Analysis
Primary	Assess the impact of LCM, LEV or no AED in patients with suspected glioma (WHO Gr I-IV) or brain metastasis on ED visits and readmissions within 30 days of MSR	Percentage of patients with an ED visit or hospital readmission within 30 days of MSR	See Section 13.4
Secondary	Assess the safety and tolerability profile of LCM and LEV	Percentage of patients who experience an adverse event of special interest within the first 30 days after MSR	See Section 13.5
Exploratory	Describe the duration of admission stays among patients treated prophylactically with LCM, LEV, or no AED	Median duration of initial admission stay for MSR	See Section 13.6.1
Exploratory	Describe the number of provider communications (email, telephone, or additional clinical visits) among patients treated prophylactically with LCM, LEV, or no AED	Frequency distribution for the number of provider communications (email, telephone, or additional clinical visits) that occurred within 30 days of MSR.	See Section 13.6.2
Exploratory	Describe the usage of intraoperative AED	Percentage of patients requiring intraoperative AED	See Section 13.6.3
Exploratory	Assess the impact of LCM, LEV, or no AED on post-procedure seizure occurrence	Percentage of patients experiencing post-procedure seizures during the 30-day post-operative phase.	See Section 13.6.4
Exploratory	Describe the frequency of changes in AED dosage, type of AED, addition or discontinuation of AED	The frequency of changes in dosages, type of AED, addition or discontinuation of AED that occur within 30 days of MSR	See Section 13.6.5
Exploratory	Evaluate patient risk factors for post-procedure seizure	Statistically significant association of specific risk factors with rate of post-procedure seizure during the 30-day post-procedure phase	See Section 13.5.6

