11.1 Adverse Events

An AE is any untoward medical occurrence in a subject receiving study drug and which does not necessarily have a causal relationship with this treatment. An AE can therefore be any unfavorable and unintended or worsening sign (including an abnormal laboratory finding) or symptom temporally associated with the use of the AED, whether or not related to use of the AED.

From the time the subject initiates AED therapy through the time the subject is off study (as defined in Section [7.3](#)), all AESIs must be recorded in the REDCap™ database AE electronic Case Report Form (eCRF). Adverse events which are not an AESI will not be collected.

AESIs will be assessed according to the Common Terminology Criteria for Adverse Events (CTCAE) version 4. If CTCAE grading does not exist for an AESI, the severity of the AESI will be graded as mild (1), moderate (2), severe (3), life-threatening (4), or fatal (5).

Attribution of AEs will be indicated as follows:

- Definite: The AE is clearly related to the study drug
- Probably: The AE is likely related to the study drug
- Possible: The AE may be related to the study drug
- Unlikely: The AE is doubtfully related to the study drug
- Unrelated: The AE is clearly NOT related to the study drug

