13.5 Secondary objectives

This study has one secondary objective which is to assess the safety and tolerability of LCM and LEV.

Adverse events will be assessed according to the NCI Common Toxicity Criteria for Adverse Events (CTCAE) version 4. For each type of toxicity, the maximum grade experienced by the patient will be summarized with frequency distributions based upon all AESIs. Of particular interest are those adverse events of special interest (AESI), as defined in section [7.1.4](#), that occur within 30 days after MSR.

The percentage of patients experiencing any grade adverse events of special interest within 30 days of MSR will be summarized in each of the 3 treatment arms, and compared using chi-square tests. If AED is shown to have fewer re-hospitalizations or ED visits, then a pairwise comparison of LCM and LEV is of particular interest.

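### No direct LCM-versus-LEV adverse-event comparison is committed to unless the primary test favours AED, although the safety objective carries no such condition

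*Protocol*

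**What the plan says.** Two places tie the LCM-LEV comparison to the efficacy result. In the rationale (Protocol 5.2.9): "If determined that AED is necessary, this study will also attempt to evaluate the side effect profile of the commonly used AED at Duke", with lacosamide then named as the comparator. In the analysis section (Protocol 13.5): "If AED is shown to have fewer re-hospitalizations or ED visits, then a pairwise comparison of LCM and LEV is of particular interest".

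Other places state the safety aim with no condition:

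- Table 1 (Protocol section 6) gives the secondary objective as "Assess the safety and tolerability profile of LCM and LEV", with the endpoint "Percentage of patients who experience an adverse event of special interest within the first 30 days after MSR". The SAP's list of secondary objectives opens with the same objective, also without condition.
- The end of Protocol 5.2.9 says: "A secondary endpoint will evaluate the safety and tolerability of LCM and LEV".
- Protocol 13.5 opens with: "This study has one secondary objective which is to assess the safety and tolerability of LCM and LEV". It then says that AESI percentages "will be summarized in each of the 3 treatment arms, and compared using chi-square tests", again without condition.

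Protocol 11.1 requires every AESI to be recorded, regardless of how the primary endpoint turns out.

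**The concern.** The plan gives two different signals about what happens to the LCM-LEV comparison when the primary test is not positive. The objective reads as unconditional. The sentences that mention comparing the two drugs are conditional. Nowhere does the protocol commit to the direct contrast after a negative primary or an interim stop for acceptance of the null.

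Whether LCM and LEV differ in side effects does not depend statistically on whether the two drugs pooled reduce ED visits and readmissions. The comparison is randomised and remains informative after a null primary. Protocol 5.2.9 itself says that AEDs are prescribed at this centre despite contrary guidelines, and that significant side effects would weigh in the risk-benefit judgement. Leaving the contrast optional until the primary result is known also invites selective reporting.

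**Working it through.** **1. The plan's own figure.** Inputs are from Protocol 13.7 and 13.8: 12% (AED) versus 25% (no AED), one-sided overall alpha 0.05, 116 patients per combined group at the final look and 58 at the interim. At the interim, reject if Z > 2.31015 and accept if Z ≤ 0.48887. At the final look, reject if Z > 1.63351. The two Z statistics are treated as bivariate normal with correlation √0.5.

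- Variance term: 0.25×0.75 + 0.12×0.88 = 0.2931.
- Final drift: 0.13/√(0.2931/116) = 2.586. Interim drift: 2.586×√0.5 = 1.829.
- P(reject at interim) = 0.315 and P(continue, then reject) = 0.488, so power is 0.803.
- Under no difference: 0.0104 + 0.0396 = 0.0500.

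For 80% power this needs N = 230 with unpooled variance or 237 with pooled variance, against the stated 232. The primary design reproduces.

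**2. How often the condition fails.** The same rule gives the table below. The 20% and 17% no-AED rates are scenarios, not figures from the documents.

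| AED vs no AED | Drift | P(primary positive) | P(not positive) |
|---|---|---|---|
| 12% vs 25% | 2.586 | 0.80 | about 20% |
| 12% vs 20% | 0.08/√(0.2656/116) = 1.672 | 0.49 | about 50% |
| 12% vs 17% | 0.05/√(0.2467/116) = 1.084 | 0.28 | about 72% |
| No effect | 0 | 0.05 | 95% |

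Simulation with binomial data agrees to within about one percentage point. Under no effect the interim acceptance boundary is met with probability Φ(0.48887) = 0.688 (67% by simulation at 12% in both groups).

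**3. Whether the unconditional test fills the gap.** Allocation is 1:1:2 (Protocol 13.8), so the final arms are 232/4 = 58, 58 and 116. The documents give no planning rates for AESIs, so the rates below are assumptions. For a chi-square across three arms the noncentrality is Σ n(p − p̄)²/[p̄(1 − p̄)].

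- *Identical drugs, LCM 40%, LEV 40%, none 20%.* Here p̄ = 0.30 and the noncentrality is (58×0.01 + 58×0.01 + 116×0.01)/0.21 = 11.05 on 2 df. The test is significant about 87% of the time (simulation), although LCM and LEV do not differ.
- *Different drugs, LCM 20%, LEV 40%, none 30%.* Here p̄ = 0.30 and the noncentrality is (58×0.01 + 58×0.01 + 0)/0.21 = 5.52 on 2 df. The test is significant 55% of the time. The direct two-arm comparison has the same noncentrality on 1 df and is significant about 66% of the time.

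So a significant three-arm result need not mean that the drugs differ, and when they do differ it is a less sensitive test of that difference. Protocol 7.1.4 also counts seizure of any grade as an AESI. Contrasts with the no-AED arm therefore mix drug toxicity with the event that the drugs are meant to prevent.

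**4. Precision of a direct comparison.** There are 58 per drug arm at full accrual and 116/4 = 29 after an interim stop. With a common assumed rate p, the 95% CI half-width for the risk difference is 1.96√[2p(1 − p)/n].

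| p | n = 58 | n = 29 |
|---|---|---|
| 10% | ±10.9 points | ±15.4 points |
| 30% | ±16.7 points | ±23.6 points |
| 50% | ±18.2 points | ±25.7 points |

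Two-sided 5% power for 10% versus 30% is 78% at 58 per arm and 48% at 29. For 10% versus 20% it is 32% and 18%.

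**The case against.** The strongest reply is that nothing is formally gated. The safety objective and its endpoint are unconditional, and AESIs are recorded, graded, tabulated by arm and tested whatever the primary shows. The conditional sentence in 13.5 marks emphasis and does not say that the comparison is otherwise omitted. The tests are in the plural, which does not rule out pairwise ones. The most clearly conditional wording sits in the rationale, not the analysis section. It is also reasonable to care most about which drug is better tolerated once prophylaxis is known to be worth giving; Protocol 5.2.8 puts its remark that LCM might be preferable for some patients under that same condition. Finally, testing a secondary contrast only after a positive primary is a recognised way to limit family-wise error.

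Much of this stands. A reader might infer that the secondary objective goes unanswered whenever the primary fails. The documents do not support that, because a profile of each drug will be reported in any case. The multiplicity argument has less force here: the protocol declares no testing hierarchy, and its chi-square tests of AESIs are already unconditional. What the reply does not supply is any statement that LCM and LEV will be compared directly after a non-positive primary.

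**Conclusion.** The point holds as a minor inconsistency with a concrete remedy. Section 5.2.9 is conditional, 13.5 mentions the pairwise contrast only for a positive primary, and the objective they serve is unconditional. No direct LCM-LEV comparison is committed to in the remaining cases, which arise about 20% of the time at the design alternative and 95% of the time under no effect. These are probabilities of a non-positive primary. They are not the chance that the safety objective fails, and they assume that the interim boundaries are followed, although Protocol 13.7 calls them guidelines.

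The finding that a three-arm chi-square cannot isolate the drug contrast does not depend on particular rates. The 87%, 55% and 66% figures do rest on assumed AESI rates.

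Two further readings should be avoided. Safety is the only secondary objective in the protocol, but the SAP lists six. The SAP text available for review is incomplete, so its silence on a pairwise analysis shows nothing.

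**What to change.** In Protocol 5.2.9, remove the condition from the sentence on the LEV-versus-LCM side-effect evaluation. In 13.5, state that LCM and LEV will be compared on the percentage of patients with an AESI within 30 days, as a risk difference with 95% CI, whatever the primary result and whether or not accrual stops at the interim. Keep the three-arm summary, and carry the same statement in the SAP.

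The cost is a sentence in each of two protocol sections and one extra table, with no new data. The drawback is low precision, above all after an interim stop with about 29 patients per drug arm. The result should therefore be presented as an estimate with its interval, and a non-significant difference should not be read as equal tolerability.
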